Part C1 initiated at a dose level of 6 mg/kg every 14 days, AIBW (selected from among the following indications: BC, NSCLC, or HNSCC). Prior to a dose escalation/de-escalation, a minimum of 3 evaluable subjects must be assessed ([Figure 6](#)). Subsequent dose escalation/de-escalation (if any) will be based upon the observed safety tolerability profile as determined in consultation with the SRC.

Part C1 will evaluate dose levels based on DLT events and TRAEs leading to treatment delay or discontinuation, including events of special interest (eg, ocular toxicity and peripheral neuropathy).

AEs that meet DLT criteria (within the 28-day DLT period) and delayed AEs that lead to treatment interruption/discontinuation within the first 6 weeks, thus encompassing the first 3 doses (DLT rate $\leq 30.0\%$; delayed AE rate $\leq 20.0\%$), will be monitored. Decision for dose escalation/de-escalation will be made by the Sponsor in consultation with the SRC guided by the decision-making table ([Appendix C](#)). The selection of MTD/RP2D with an every 14-day dosing regimen will be based predominantly on safety and may take other factors into account such as PK/PD and clinical activity.

Subjects who discontinue study drug administration for reasons other than DLTs may be replaced to ensure the minimum number of subjects required for DLT evaluation is enrolled.

3.7 Part C2 (CX-2009 Monotherapy): Dose Expansion at the MTD/RP2D for Every 14-Day Dosing Regimen in Selected Tumor Types (Maximum n ≤ 200)

To explore efficacy of CX-2009 for every 14-day dosing regimen, indication-specific expansion cohorts will be opened to obtain preliminary evidence of clinical activity. Part C2 will enroll up to a total of 40 subjects each in 1 or more of the tumor types listed in [Table 4](#). These tumor types have been selected for their responsiveness to MTIs and general availability of lesion safe to be biopsied. Part C2 may be initiated as soon as the MTD/RP2D for the 14-day regimen is defined in consultation with the SRC and will only be initiated if, after the review of dose escalation data (Part C1), an every 14-day dosing regimen is considered for further development.

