Allocation of Subjects Between Parts C, D, and E. In case Parts C, D, and E are open for enrollment concurrently and subjects meet the eligibility criteria for all parts, the Sponsor in conjunction with the Principal Investigator will determine to which part the subjects are allocated. The Sponsor will determine which tumor types will be selected for additional evaluation for Parts B, C2, D2, and E2.

Note: Dose expansion for CX-2009 monotherapy may occur under the every 21-day dosing regimen (Part B) and/or the every 14-day dosing regimen (Part C2), depending on available data from Parts A, A2, and C1. Selection of the regimen for dose expansion will be made in consultation with the SRC.

3.8 Part D1 (CX-2009 + CX-072): Dose Escalation/De-escalation and Determination of MTD/RP2D for Every 14-Day Dosing Regimen in Selected Tumor Types (n ≤ 24)

Part D1 is only open to those countries in which the Health Authority permits the combination of CX-2009 and CX-072 to be investigated. The dose of CX-072 will be fixed at the RP2D (800 mg every 14 days). The starting dose for CX-2009 will be set at the every 14-day monotherapy RP2D as determined in Part C1. Lower starting doses may be used based on emerging safety data and in consultation with the SRC. The mTPI-2 design will be used to determine the MTD/RP2D for this schedule. The following cohort's dose will be increased or decreased according to the defined dose escalation rules based upon the observed safety tolerability profile as determined in consultation with the SRC. Prior to a dose escalation/de-escalation, a minimum of 3 evaluable subjects must be assessed per the mTPI-2 algorithm ([Figure 6](#)). Part D1 will enroll subjects in 1 or more of the tumor types listed in [Table 4](#). The tumor types have been selected for their responsiveness to MTIs and general availability of lesion safe to be biopsied.

Part D1 will evaluate dose levels based on DLT events and TRAEs leading to treatment delay or discontinuation, including events of special interest (eg, ocular toxicity and peripheral neuropathy).

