Part E1 is only open to those countries in which the Health Authority permits the combination of CX-2009 and CX-072 to be investigated. The dose of CX-072 will be fixed at the RP2D (1200 mg every 21 days). The starting dose of CX-2009 will be 7 mg/kg (the every 21-day monotherapy RP2D as determined in Parts A/A2). Lower starting doses may be used based on emerging data and in consultation with the SRC. The mTPI-2 design will be used to determine the MTD/RP2D for this schedule. The following cohort's dose will be increased or decreased according to the defined dose escalation rules based upon the observed safety tolerability profile as determined in consultation with the SRC. Prior to a dose escalation/de-escalation, a minimum of 3 evaluable subjects must be assessed per the mTPI-2 algorithm ([Figure 6](#)). Part E1 will enroll subjects in 1 or more of the tumor types listed in [Table 4](#). The tumor types have been selected for their responsiveness to MTIs and general availability of lesion safe to be biopsied.

Part E1 will evaluate dose levels based on DLT events and TRAEs leading to treatment delay or discontinuation, including events of special interest (eg, ocular toxicity and peripheral neuropathy).

AEs that meet DLT criteria (within the 21-day DLT period) and delayed AEs that lead to treatment interruption/discontinuation within the first 6 weeks, thus encompassing the first 3 doses (DLT rate $\leq 30.0\%$; delayed AE rate $\leq 20.0\%$), will be monitored. Decision for dose escalation/de-escalation will be made by the Sponsor in consultation with the SRC guided by the decision-making table ([Appendix C](#)). The selection of MTD/RP2D will be based predominantly on safety and may take other factors into account such as PK/PD and clinical activity.

Subjects who discontinue study drug administration for reasons other than DLTs may be replaced to ensure the minimum number of subjects required for DLT evaluation is enrolled.

**3.11 Part E2 (CX-2009 + CX-072):
Dose Expansion for Every 21-Day Dosing Regimen in Selected Tumor Types
(Maximum n ≤ 200)**

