9.1 Populations

For assessment of MTD/RP2D, the population will be based on subjects who are evaluable for DLT determination (a “DLT-evaluable” subject is defined as having received at least 1 dose of CX-2009 (or CX-2009 and CX-072) and completed the full DLT observation period (either 21 or 28 days depending on the schedule) or a subject who has withdrawn from the study drug due to a drug-related toxicity. Subjects who are not DLT evaluable may be replaced in the cohort.

For assessment of efficacy (Parts B, C2, D2 and E2), subjects must have undergone at least 1 on-study imaging assessment. Subjects who die prior to his/her first on-study scan will not be counted as evaluable for this assessment.

The efficacy evaluable group for Parts D2 and E2 will include only those subjects who are determined to be PD-L1 positive.

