9.2. Dose Escalation Guidelines

Until a DLT or treatment related \geq Grade 2 related toxicity is observed requiring cohort expansion, single-subject cohorts may be explored at the beginning dose levels. In this way, the number of subjects exposed to subtherapeutic doses will be minimized.

In this setting, as soon as a DLT is observed in a single-subject cohort, or a subject experiences a \geq Grade 2 study drug-related adverse event (AE), or cohort escalation reaches a starting dose level as defined in the module, cohorts will be enrolled using the standard 3 + 3 design. Cohort escalation may only take place after all individuals in a given cohort have reached the end of the DLT window and the Sponsor has approved further dose escalation.

Subjects who withdraw from the study for any reason during the DLT evaluation interval for reasons other than a DLT will be replaced. Dose escalation will proceed between cohorts according to the schema outlined in the module (or with smaller increments if significant AEs are observed).

After the rate of DLTs has been defined for a specific dose in 3 or 6 subject cohorts, additional subjects may be accrued at any dose level to better define the relationship between dose and emerging safety of efficacy signals, as specified in the module.

Escalation of the Probody Tx as monotherapy will be initiated first, and continue until the pre-specified top dose is administered safely or the maximum tolerated dose (MTD) is defined, whichever comes first.

Separate tracks of dose escalation of each combination regimen within a module, may also be conducted. The timing of initiation of the combination evaluation will differ, depending on the Probody Tx under evaluation (and as characterized in the relevant module). Initiation of combination evaluation could be as early as the time of successful clearing of monotherapy Cohort 2 and after consultation with the SRC. The dose of the combination agent(s) will be defined in each Probody Tx-specific module.

Once combination dose escalation has been initiated, it will proceed independently of the monotherapy escalation and continue until the pre-specified top doses for each agent are administered safely or the MTD is defined, whichever comes first. However, at the time of any dose escalation decision, the Sponsor and SRC will review available safety data from the monotherapy and/or combination cohort before a decision to escalate is made.

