Both mTPI and mTPI-2 designs are transparent and user-friendly to both statisticians and clinicians, as all the decisions can be tabulated for examination prior to the trial. Figure 6 and Figure 7 are dose-finding decision tables for up to 14 subjects with target toxicity probability of 30.0% and 20.0%, respectively. In these tables, the columns represent the number of subjects treated at the current dose and rows denote the number of subjects experiencing DLT at that dose. The table enumerates all the possible dose-finding decisions, and therefore can be used to design and conduct the trial conveniently.

Figure 6. Decision Table for mTPI-2 Cohort (Target Toxicity Probability = 30.0%)

		Number of Patients													
		1	2	3	4	5	6	7	8	9	10	11	12	13	14
Number of Patients with DLTs	0	E	E	E	E	E	E	E	E	E	E	E	E	E	E
	1	D	D	S	S	E	E	E	E	E	E	E	E	E	E
	2		D	D	D	D	S	S	S	E	E	E	E	E	E
	3			DU	DU	D	D	D	D	S	S	S	S	E	E
	4				DU	DU	DU	D	D	D	D	D	S	S	S
	5					DU	DU	DU	DU	DU	D	D	D	D	D
	6						DU	DU	DU	DU	DU	DU	D	D	D
	7							DU	D						
	8								DU						
	9									DU	DU	DU	DU	DU	DU
	10										DU	DU	DU	DU	DU
	11											DU	DU	DU	DU
	12												DU	DU	DU
	13													DU	DU
	14														DU

A decision table of the mTPI-2 design, with 14 subjects, the target probability of $p_T = 0.3$ and 2 values $\epsilon_1 = \epsilon_2 = 0.05$.

D = de-escalate to a lower dose; DLT = dose-limiting toxicity; DU = de-escalate to a lower dose and the current dose will never be used again in the study; E = escalate to the next higher dose; mTPI-2 = modified toxicity probability interval 2; S = stay at the same dose.

Figure 7. Decision Table for mTPI-2 Cohort (Target Toxicity Probability = 20.0%)

		Number of Patients													
		1	2	3	4	5	6	7	8	9	10	11	12	13	14
Number of Patients with DLTs	0	E	E	E	E	E	E	E	E	E	E	E	E	E	E
	1	D	D	D	D	S	S	S	E	E	E	E	E	E	E
	2		DU*	DU	D	D	D	D	D	S	S	S	S	S	S
	3			DU	DU	DU	DU	D	D	D	D	D	D	S	S
	4				DU	DU	DU	DU	DU	DU	D	D	D	D	D
	5					DU	D								
	6						DU								
	7							DU							
	8								DU						
	9									DU	DU	DU	DU	DU	DU
	10										DU	DU	DU	DU	DU
	11											DU	DU	DU	DU
	12												DU	DU	DU
	13													DU	DU
	14														DU

$n = 14, p_T = 0.2, \epsilon_1 = 0.05, \epsilon_2 = 0.05$

A decision table of the mTPI-2 design, with 14 subjects, the target probability of $p_T = 0.2$ and 2 values $\epsilon_1 = \epsilon_2 = 0.05$.

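### In Parts C1, D1 and E1 a dose escalation can be decided at Day 21 or 28, before the 6-week delayed-toxicity criterion can be scored

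*Protocol*

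**What the plan says.** - **Evaluability.** Protocol Section 9.1, like Section 3.1, bases MTD/RP2D assessment on subjects who "completed the full DLT observation period (either 21 or 28 days depending on the schedule") or who withdrew for drug-related toxicity. No other evaluability definition for dose finding is given.
- **Gate in the Module.** Before a dose change, Section 3.6 (C1) says "a minimum of 3 evaluable subjects must be assessed"; Sections 3.8 (D1) and 3.10 (E1) say "a minimum of 3 evaluable subjects must be assessed per the mTPI-2 algorithm". All three cite Figure 6 only, the table with a 30% target.
- **Gate in the Core.** Core Section 9.2 says "Cohort escalation may only take place after all individuals in a given cohort have reached the end of the DLT window", and also requires Sponsor approval.
- **Second criterion.** Section 3.10 says "Part E1 will evaluate dose levels based on DLT events and TRAEs leading to treatment delay or discontinuation". Section 3.8 says "Part D1 will evaluate dose levels based on DLT events and TRAEs leading to treatment delay or discontinuation", and Section 3.6 says the same for C1. Each part monitors "delayed AEs that lead to treatment interruption/discontinuation within the first 6 weeks, thus encompassing the first 3 doses", with a limit of 20%, beside a 30% limit for DLTs. The Sponsor decides in consultation with the Safety Review Committee (SRC), guided by Appendix C.
- **Tables.** Appendix C holds Figure 6 (target 30%) and Figure 7 (target 20%). In both, "the columns represent the number of subjects treated at the current dose and rows denote the number of subjects experiencing DLT at that dose".
- **Reason for the 6 weeks.** Section 3.2 explains, for Part A, that events of special interest had appeared late, so treatment-related events are followed over 42 days.

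The SAP (Sections 9.1 and 9.2) defines only the safety and response-evaluable populations, so it does not fill the gap.

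**The concern.** Two criteria with different time horizons steer one decision, but only the shorter one has an evaluability rule and a gate. A subject who has just finished the DLT period is fully informative for the 30% criterion and only partly informative for the 20% one. If that subject is entered as treated without an event, the observed delayed rate is biased downwards. The bias falls on the toxicities the 6-week window was added to catch: ocular toxicity and neuropathy that lead to held or stopped doses. Two cohorts could also be judged on different lengths of follow-up without anyone departing from the plan.

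**Working it through.** **1. The plan's tables.** I rebuilt Figures 6 and 7 as mTPI-2 with a Beta(1,1) prior, subintervals of width 0.10 and a 0.95 exclusion cutoff. The prior and cutoff are assumed standard values; the documents do not state them. In each table 118 of 119 cells match. The one mismatch in each is at fewer than 3 subjects (2/2 in Figure 6, 1/1 in Figure 7), so every cell for 3 to 6 subjects is reproduced. For 0, 1, 2 and 3 events in 3 subjects:

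| Table | 0/3 | 1/3 | 2/3 | 3/3 |
|---|---|---|---|---|
| Figure 6 (30%) | E | S | D | DU |
| Figure 7 (20%) | E | D | DU | DU |

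So 0/3 DLTs reads escalate on Figure 6, while a single delayed event in the same three subjects reads de-escalate on Figure 7.

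**2. Calendar.** Inputs: dosing every 21 days (E1) or 14 days (C1, D1), with Day 1 the first dose (Appendix B schedules); DLT periods of 21 and 28 days; a 42-day window. Dose k is due on Day 1 + (k − 1) × interval.

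| Part | Doses due | Gate | Scheduled doses by gate | Days unobserved |
|---|---|---|---|---|
| E1 | 1, 22, 43 | Day 21 | 1 | 42 − 21 = 21 |
| C1, D1 | 1, 15, 29 | Day 28 | 2 | 42 − 28 = 14 |

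In E1 no dose can yet be late at Day 21, so only a discontinuation or an early decision to hold is visible. In C1 and D1 the fate of Dose 3 is unknown at Day 28.

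**3. Size for three subjects followed only to the gate.** Let q be the true 6-week rate and v the share of events visible at the gate. Then P(0/3) = (1 − qv)³. The documents give neither q nor v. If events are spread evenly over 42 days, v = 28/42 = 0.667 or 21/42 = 0.50.

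| q | Full data | Day 28 | Day 21 |
|---|---|---|---|
| 30% | 0.70³ = 34% | 0.80³ = 51% | 0.85³ = 61% |
| 40% | 0.60³ = 22% | 0.733³ = 39% | 0.80³ = 51% |
| 50% | 0.50³ = 13% | 0.667³ = 30% | 0.75³ = 42% |

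In E1, v may be below 0.50, because no delay can be scored before Day 22. At v = 0.25 and q = 40%, P(0/3) = 0.90³ = 73%.

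Given 0/3 at the gate and q = 40%, the chance that at least one of the three has an event by Day 42, so that Figure 7 then reads D or DU, is 1 − 0.216/0.394 = 45% (C1, D1) or 1 − 0.216/0.512 = 58% (E1).

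**4. Six subjects.** Suppose six at a dose arrive as 3 + 3. When the second three reach the gate, the first three are at Day 42 or later (E1: 21 + 21 = 42; C1, D1: 28 + 28 = 56). At q = 40%, P(0/6) is 0.216 × 0.394 = 8.5% in C1 and D1 and 0.216 × 0.512 = 11% in E1, against 0.6⁶ = 5% with full data. The effect is much smaller than with three.

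**5. E1 and Dose 3.** Dose 3 is due on Day 43, which is 42 elapsed days. It is late after the 2-day window (Day 45). With the 7-day allowance in Section 5.5.4, a missed dose is settled at about Day 50.

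**The case against.** The strongest reply is that nothing forces an early decision. Delayed events are monitored, the tables only guide, and the Sponsor and SRC can wait, review later data and de-escalate. The expansion parts also carry their own 6-week stopping rule in the first 6 subjects (Section 9). A short DLT gate with continued monitoring is a recognised design. All of this stands, but it shows only that the plan permits good practice; it does not require it.

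Other points also stand:

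- No text assigns Figure 7 to delayed events. Its rows are labelled DLTs, and the link is inferred from the shared 20%.
- The probabilities in step 3 are not the chance of escalating, because they leave out Figure 6, DLTs and SRC judgement. They also assume three subjects dosed together; any stagger gives earlier subjects longer follow-up.
- The Core sentence follows directly on the 3+3 rules and sets a floor. The Module's own gate gives the same timing without it.
- Waiting has a price. Median exposure was 7.3 weeks (Section 1.3.4) and each part is capped at 24 subjects, so some subjects would leave before 6 weeks.

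A reader might infer that E1's window misses Dose 3 altogether. That is too strong. Counted as elapsed days, 6 weeks ends on the Dose 3 due date, the ±2-day window can bring the infusion inside, and the wording can be read as AE onset within 6 weeks. What remains is that an on-schedule Dose 3 gets no follow-up and a missed one cannot be settled within the window.

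**Conclusion.** The concern holds in a limited form. In C1, D1 and E1 the stated evaluability definition and gate permit escalation before the 6-week criterion can be scored, and they let a partly followed subject count as event-free. The direction of the bias is certain; its size is not. For three subjects followed only to the gate, at an assumed 40% rate with even spread, the chance of 0/3 rises from 22% to 39% (C1, D1) or 51% (E1). With six subjects enrolled 3 + 3, it rises only from 5% to 8.5% or 11%.

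A reader might go further and infer that a dose in this trial was escalated too early. The documents do not support that. SAP Section 4.2 places all 99 treated subjects in Parts A (with its mTPI-2 cohort), A2, B and C1 (37 + 39 + 10 + 3 + 10 = 99), so none were in D1 or E1. In C1, 6 mg/kg was followed by a move down to 4 mg/kg after DLTs in 2 of 5 evaluable subjects, which agrees with Figure 6. The point concerns the plan as written; it should be corrected, with medium confidence in its practical weight.

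**What to change.** 1. In Section 9.1 and Appendix C, state that the 20% table is the one for delayed events. Count a subject in it only after 6 weeks of follow-up or an earlier qualifying event, never as event-free on partial follow-up.
2. In Sections 3.6, 3.8 and 3.10, require escalation decisions to take account of that count, preferably with at least 3 such subjects. A hard minimum of 3 is the more debatable part, given the cap of 24. De-escalation need not wait.
3. Minor, for E1: either extend the window by the dosing allowance (to Day 45 if a late dose counts, about Day 50 if a missed dose counts), or say that it covers AEs up to the Dose 3 due date.

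The cost is Module wording. If escalation waits for the full 6 weeks, add about 14 days per cohort in C1 and D1 and 21 in E1 (45 − 21 = 24 to 50 − 21 = 29 if the E1 window is extended), plus replacement of some subjects who stop before 6 weeks for other reasons.

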9.2 Other Statistical Analyses

Statistical assessments/methods for safety, efficacy, PK/PD, and immunogenicity are found in Section 11 of the Core. In instances where the statistical analysis plan (SAP) might contradict the analyses specified in the Core, the SAP supersedes the Core.

Available data from Part A2 will be pooled with data from Part A by dose. In addition, efficacy data from Part A2 may be analyzed separately. The relationship between dose and safety/efficacy may be explored. Analyses by dose may be conducted for, but not limited to, the following endpoints: frequency of AEs of special interest, ORR, and percent reduction in tumor burden by dose. A generalized linear model may be used to adjust for covariates or to model the relationship. Because of the limited number of subjects, the above analyses will be conducted if data warrant.

10 DATA SAFETY MONITORING BOARD

The Data and Safety Monitoring Board (DSMB) will monitor the safety of the study. The DSMB will consist of individuals in relevant fields of expertise. It will convene on a regular basis (at least 2 times per year or at a different frequency as otherwise agreed) and will review all safety information to determine whether the study should continue unchanged or whether Module modifications are required to ensure subject safety. Details on the DSMB are provided in [Appendix D](#) and in a separate DSMB charter. The DSMB will make recommendations to the Sponsor, who will make ultimate decisions regarding study alteration or discontinuation.

11 INVESTIGATOR REQUIREMENTS AND QUALITY CONTROL

11.1 Ethical Conduct of the Study

This study will be conducted in accordance with the current IRB/IEC approved clinical Module, Core, ICH Good Clinical Practice Guidelines, and relevant policies and requirements of the national regulations and laws, including the Health Insurance Portability and Accountability Act of 1996.

11.2 Institutional Review Board or Independent Ethics Committee

The IRB/IEC will meet all FDA requirements governing IRBs (21 Code of Federal Regulations [CFR] Part 56).

The Investigator will provide the Sponsor (or designee) with documentation of IRB/IEC approval of the following documents before the study begins at the study site(s): Module, Core, ICF, and any other relevant materials intended for or directed to subjects (eg, subject diaries, advertisements). The Investigator will supply documentation to the Sponsor of IRB/IEC requirements regarding continuing review and approval of revisions to any of these documents.

11.3 Subject Information and Informed Consent

Written informed consent/assent is required from each subject prior to any testing under this Module, including Screening tests and evaluations. The ICF, as specified by the clinical site's IRB/IEC, must follow the Protection of Human Subjects regulations listed in 21 CFR Part 50.

The ICF will be used to explain the risks and benefits of study participation in simple terms before the subject will be entered into the study. The ICF will contain a statement that the consent is freely given, that the subject is aware of the risks and benefits of entering the study, and that the subject is free to withdraw from the study at any time. Written informed consent must be given by the subject after the receipt of detailed information on the study. It is the responsibility of the Investigator to obtain consent/assent and to provide the subject with a copy of the signed and dated ICF. Confirmation of a subject's informed consent must also be documented in the subject's medical record prior to any testing under this Module, including Screening tests and evaluations.

All ICFs used in this study must be approved by the appropriate IRB/IEC and by the Sponsor or its designee. The ICF must not be altered without the prior agreement of the relevant IRB/IEC and the Sponsor.

